5.4. Procedures for Monitoring Patient Compliance

The investigator will be responsible for monitoring patient compliance. A check of study drug compliance will be performed during each visit after the initial dispensation of study drug; and study drug accountability records will be completed. If the investigator or the sponsor determines that the patient is not in compliance with the study protocol, the investigator and the sponsor should determine whether the patient should be withdrawn. The IEC/IRB should be notified.

5.5. Total Blood Volume

The total blood volume to be collected for each patient in this study is approximately 164.5 mL ([Table 3](#)).

Table 3: Blood Volumes

Type of samples	Volume per sample (mL)	Total number of samples	Total volume (mL)
Clinical laboratory	15.5	5 ^a	77.5
Biomarkers	18	4	72
ADA	5	3	15
Total	38.5	12^a	164.5

^a A single clinical laboratory sample will be collected from the healthy control subjects, at the screening visit.

ADA=anti-drug antibody.

6. ASSESSMENT OF EFFICACY

6.1. Primary Efficacy Measure and Justification

The primary efficacy measure for this study is the change in GLG as assessed by PET/CT. Part 1 of the study will validate this measure by comparing this assessment between HC subjects and patients with eosinophilia asthma. In Part 2, only patients with eosinophilic asthma will be assessed for GLG at 2, 4, and 6 weeks, after randomization to placebo or treatment with a single dose of reslizumab.

6.1.1. Positron Emission Tomography/Computerized Tomography Scans

Patients must fast for 8 hours prior to the scan. Blood glucose level will be measured before the administration of FDG. Blood glucose level should not exceed 150 mg/dL at the time of injection. Whole-body, head-to-toe PET/CT image acquisition will begin about 120 minutes after iv administration of 7 mCi of the radioisotope fluorine-18 (¹⁸F)-FDG. PET/CT image acquisition will take 30 to 40 minutes. In total, patients will spend about 3 hours in the PET center per each imaging visit. Patients will be asked to return in 2 days for a repeat FDG-PET/CT scan to be used as technical replicates in Part 1. Because ¹⁸F has a half-life of 109 minutes and is effectively fully decayed within a few hours of administration, FDG will be re-administered during the follow up visits and PET/CT imaging will be performed following the same protocol described above.

Each FDG-PET/CT scan will deliver about 800 millirem (mrem) of radiation to the patient. Because patients will undergo 5 PET/CT scans, it is estimated that patients will receive a total radiation of 4000 mrem, which is within yearly limits set by the [REDACTED]

To minimize radiation-absorbed dose to the bladder, adequate hydration should be encouraged to permit frequent voiding during the first few hours after iv administration of FDG injection. This may be achieved by having patients drink at least an 8 oz glass of water prior to drug administration. To help protect themselves and others in their environment, patients should take the following precautions for 12 hours after injection: whenever possible, a toilet should be used and should be flushed several times after each use and hands should be washed thoroughly after each voiding or fecal elimination. If blood, urine or feces soil clothing, the clothing should be washed separately.

6.1.2. Image Analysis

Axial, sagittal, and coronal PET reconstructions will be interpreted, with and without attenuation correction, using non-contrast CT images for anatomical correlation. The investigators plan to measure global and regional inflammation within the lung, lymph nodes and bone marrow by utilizing quantitative parameters based on both volume and SUV. SUV is a well validated measure which normalizes FDG uptake by any particular object/tissue volume by the administered dose and either total body weight or total body surface area. Regions of interest (ROIs) will be drawn manually around the outer boundaries of the lung on every transverse slice passing through the lung on fused FDG PET/CT images from each subject. The trachea and main

stem bronchi will be excluded from the ROIs to capture only the inflammation in the lung parenchyma. Lung sectional mean standardized uptake value (sSUV mean) and the area of the lung ROI will be recorded from each slice. Subsequently, the sLV will be calculated from each slice by multiplying the lung ROI area (in centimeters squared) by 0.4 (slice thickness 4 mm). The sLG will be determined by multiplying sLV and lung sSUV mean from each slice. The LV will be calculated by adding all the sLV from slices passing through the lung, and the GLG will be determined by adding all the sLG from slices passing through the lung. Finally, the lung SUV mean will be calculated by dividing the GLG by the LV. Applying this methodology to different tissues or regions of the lungs will allow us to determine average and global SUV measures for the following tissues: whole lung parenchyma, right and left lung parenchyma, trachea, bronchi, and right and left bronchi. These regions will be delineated in the CT images by using the image segmentation techniques. These tissue volumes will be registered with the PET images as outlined below for the estimation of SUVs within these regions. Similar methodology will be applied to the lymph nodes and bone marrow.

6.1.3. Calculations

The radiology center will determine the following:

GLG is the total FDG uptake in the whole lung.

An ROI is drawn around lung boundary in each axial slice. SUVmean and area of each ROI is recorded. Using the formula: area*slice thickness the volume of each slice is calculated. Then SUVmean of each slice is multiplied by the volume of the corresponding slice, which will represent the total FDG uptake in one slice. This number for each slice is summed together to provide GLG of that lung.

$$GLG = \sum_1^n (area * slice\ thickness * SUVmean)$$

n=number of slices

Intra-patient variability (reproducibility measure):

Below is the calculation to determine the intra-patient variability between PET/CT scans as measured by GLG for HCs and patients with eosinophilic asthma. The accepted variability within each group is $\leq 10\%$ and will be as follows:

Relative difference of GLG=(GLG2-GLG1)/GLG1

Relative difference of GLG=(GLG4-GLG3)/GLG3

1= First time point (HCs)

2= Second time point (HCs)

3= First time point (patients with eosinophilic asthma)

4= Second time point (patients with eosinophilic asthma)

Variability between HC group and individual patients with eosinophilic asthma:

The planned method to assess whether the difference in GLG (Δ GLG) between HC subjects, as a group, and individual patients with eosinophilic asthma is $\geq 5\%$ and will be as follows:

For Females:

Relative difference of GLG=(GLG6_i-GLG5f)/GLG5f

For Males:

Relative difference of GLG=(GLG6_i-GLG5m)/GLG5m

5=average of 1 and 2

6=average of 3 and 4

GLG6_i will be calculated for each individual patient using his/her two measurements, and if that amount is $\geq 5\%$, than the patient will be randomized.

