Part 2 will be a 7-week double-blind evaluation of patients with severe asthma with an eosinophilic phenotype that have been randomized to receive a single dose of either placebo or reslizumab at 3 mg/kg.

Part 1

Within 7 days (±3 days) of eligibility being confirmed, participants will have a PET/CT scan as per the PET/CT scan protocol described in Part 2 below. Participants will return to the [REDACTED] [REDACTED] 7 days (±3) after the first PET/CT scan (taken during visit 2) for a second PET/CT scan following the same procedures described above. HC subjects (n=5) may also have a second sputum induction and blood sample collection at [REDACTED] with 1 day of the 2nd PET/CT scan, if feasible (preferred but not required). Healthy subjects will be considered

complete at this time. Only after all 5 HCs have completed the study will patients with asthma be screened.

If the relative difference in GLG (based on the average of the 2 measurements) between healthy and asthma patients will be $\geq 5\%$, then the asthma patients will be randomized.

A 10% variability (measured as relative difference between first measurement and second measurement) between PET/CT scans as measured by GLG within each group will be considered as the maximum allowed variability. The part 1 criteria have been set at these levels to observe a difference between the healthy subjects and patients with asthma and to ensure intra-group reproducibility; the criteria are based on the investigators' prior experience. If these exploratory criteria are not met (eg, 8 or more patients do not meet the criteria to enter Part 2 [inclusion criteria k and l]), then the study will be reevaluated.

Part 2

If eligible (eg, if inter- and intra-group GLG variability criteria are met), patients will be randomized. This may occur at any time after confirmation of eligibility and up to the time of dosing. Patients will return to [REDACTED] for baseline clinical, serological, and biochemical measures at the Clinical Research Center (CRC) according to standard procedures. Once these are completed, patients will receive either placebo or reslizumab and will receive the infusion at [REDACTED]. Any new serious adverse events, reslizumab-related adverse events, and new concomitant medications will be reported.

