^a screening visit (visit 1) will take place up to 21 days before the V2 visit. It is understood that not all procedures can be completed on the same day. In particular, the patient may need to return to satisfy the medication hold for screening pre-bronchodilator FEV₁.

^b Physical examination, vital signs, blood samples, and ECG should be obtained before spirometry procedures and IP administration.

^c Vital signs measurements will include blood pressure, pulse, respiratory rate, body temperature, and blood oxygen saturation (SpO₂). Height and weight measurements are required only at screening visit.

^d The clinical chemistry will include a complete metabolic panel.

^e A serum β-HCG pregnancy test will be performed at V1 only, for all participating women of childbearing potential. Urine β-HCG tests will be performed, for all participating women of childbearing potential, at V2, V3, V5, V6, and V7, prior to performance of PET/CT scan.

^f Hematology will include a complete blood count with differential. The results of the differential blood tests performed after study drug administration will be blinded. If there is a medical need to review these results, the investigator will contact the medical monitor.

^g The results of the sputum eosinophil assessments performed after study drug administration will be blinded. If there is a medical need to review these results, the investigator will contact the medical monitor.

^h A complete urinalysis will be performed at the screening visit, visit 4, and visit 7; a urine dipstick test for glucose will be performed prior to each PET/CT scan.

ⁱ Patients should be observed for 1 hour following completion of PET/CT scan.

^j Blood samples for ADA assessment will be collected at baseline (before study drug administration) and other scheduled time points, and upon observation of any severe hypersensitivity reaction (eg, anaphylaxis).

^k Randomization can occur any time from determining that the patient qualifies for Part 2 up to study drug infusion. Patient qualification is based on meeting both of the following 2 steps: 1) $\Delta\text{GLG} \leq 10\%$ versus V2 [for reproducibility] and 2) $\Delta\text{GLG} \geq 5\%$ versus HC [for signal] to study drug infusion.

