3.14.3. Procedures During Study Drug Treatment

3.14.3.1. Part 2 (Week 1 [Visit 4])

Randomization may occur at any time from determining that the patient qualifies for Part 2 up to study drug infusion. Patient qualification is based on meeting both of the following 2 steps:

1) $\Delta GLG \leq 10\%$ versus V2 (for reproducibility) and 2) $\Delta GLG \geq 5\%$ versus HC (for signal).

Patients will be assigned a permanent, unique randomization number and a treatment number. These 2 assigned numbers will be entered in the CRF.

On Part 2, day 1 (within 72 hours of the PET/CT scan), the following procedures will be performed:

- Inquire about adverse events

- Inquire about concomitant medication usage
- Perform brief physical examination
- Assess vital signs (as described in Section 3.14.1)
- Perform urine pregnancy test (for women of child bearing potential)
- Perform clinical laboratory tests (chemistry, urinalysis, and hematology).
- Collect sputum sample.
- Administer the AQLQ+12
- Collect blood sample for serum ADA assay
- Collect blood sample for biomarkers analyses
- Perform spirometry

Once the above procedures have been performed, study drug infusion will occur. Any adverse events that occurred, or concomitant medications that were administered, during the visit will be recorded.

Observe patients for 1 hour after completion of study drug infusion.

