4.1. Patient Inclusion Criteria

Healthy subjects and patients may be enrolled in this study only if they meet all of the following criteria:

- a. Male or female, 18 through 50 years of age.
- b. Females that are either surgically sterile, are 2 years postmenopausal, or have a negative pregnancy test beta-human chorionic gonadotropin at screening (serum) and all PET/CT imaging visits (urine).
- c. Females of childbearing potential (not surgically sterile or 2 years postmenopausal), have to use a medically accepted method of contraception and have to agree to continue to use of this method for the duration of the study and for 5 months after study drug administration. Acceptable methods of contraception include barrier method with spermicide, abstinence, intrauterine device (IUD), or steroid contraceptive (oral, transdermal, implanted, and injected). Note: partner sterility alone is not acceptable for inclusion in the study.
- d. Subjects and patients with less than 10-pack year history of smoking.

Patients may be included in the study only if they also meet all of the following, additional criteria:

- e. Male or female, 18 through 50 years of age, with a previous diagnosis of asthma.
- f. Patients taking inhaled fluticasone at a dosage of at least 440 mcg daily, or equivalent.
- g. The patient's baseline asthma therapy regimen (including, but not limited to, inhaled corticosteroids, leukotriene receptor antagonists, 5-lipoxygenase inhibitors, or cromolyn) must be stable for 30 days prior to screening and judged by their treating physician to be able to continue without dosage changes throughout the study.
- h. Patients with a blood eosinophil level of at least 400/ μ L at screening. Patients with a blood eosinophil level below 400/ μ L will be given 2 additional screening opportunities to determine blood eosinophil levels.
 - i. Patients with airway reversibility of at least 12% to β -agonist administration.
 - j. Patients with an ACQ score of at least 1.5 at either screening or baseline visits.

Patients may be included in Part 2 of the study only if they also meet the following, additional criteria:

- k. the intrapatient reproducibility, taken as sequential GLG measures on visits 2 and 3 (Table 2), differs by only $\leq 10\%$

1. the intragroup variability (signal window), taken as a difference in the 2 subcriteria (below) to be $\geq 5\%$:

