This study is designed in 2 parts. Part 1 is a validation step whereby the sponsor wishes to determine (1) the intra-patient reproducibility in the GLG measure, and (2) the difference in the GLG measure between individual patients with severe asthma with an eosinophilic phenotype (1-by-1) and the entire HC group. Limits for both the reproducibility within patients and difference between the 2 groups have been provided by subject matter experts. Part 2 will be a 7-week double-blind evaluation of patients with severe asthma with an eosinophilic phenotype that have been randomized to receive a single dose of either placebo or reslizumab at 3 mg/kg.

#### Part 1

Within 7 days ( $\pm 3$  days) of eligibility being confirmed, participants will have a PET/CT scan as per the PET/CT scan protocol described in Part 2 below. Participants will return to the [REDACTED] 7 days ( $\pm 3$ ) after the first PET/CT scan (taken during visit 2) for a second PET/CT scan following the same procedures described above. HC subjects (n=5) may also have a second sputum induction and blood sample collection at [REDACTED] within 1 day of the second PET/CT scan, if feasible (preferred but not required). Healthy subjects will be considered complete at this time. Only after all 5 HCs have completed the study will patients with asthma be screened.

If the relative difference in GLG (based on the average of the 2 measurements) between healthy subjects and asthma patients will be  $\geq 5\%$ , then the asthma patients will be randomized. A 10%

variability (measured as relative difference between first measurement and second measurement) between PET/CT scans as measured by GLG within each group will be considered as the maximum allowed variability. The Part 1 criteria have been set at these levels to observe a difference between the healthy subjects and patients with asthma and to ensure intra-group reproducibility. The criteria are based on the investigators' prior experience. If these exploratory criteria are not met (i.e., 8 or more asthma patients do not meet the criteria to enter Part 2 [inclusion criteria k and l]), then the study will be reevaluated.

Detailed by-visit information for Part 1 are provided in sections 3.14.1 and 3.14.2 of the protocol.

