### 6.2. Primary Efficacy Endpoint and Analysis

#### 6.2.1. Definition

The primary efficacy measure for this study is the change in GLG as assessed by PET/CT.

Part 1 of the study will validate this measure by comparing this assessment between HC subjects and patients with eosinophilia asthma.

In Part 1, the primary efficacy endpoint is the intra-patient variability (reproducibility measurement) in each group and inter-group variability between HC group and individual patients with eosinophilic asthma.

In Part 2, only patients with eosinophilic asthma will be assessed for GLG at 2, 4, and 6 weeks, after randomization to placebo or treatment with a single dose of reslizumab.

In Part 2, the primary efficacy endpoint is the change from baseline to week 4 in GLG ( $\Delta$ GLG).

The radiology center at [REDACTED] will determine the following:

GLG is the total FDG uptake in the whole lung.

A region of interest (ROI) is drawn around lung boundary in each axial slice. SUVmean and area of each ROI is recorded. Using the formula:  $area * slice\ thickness$ , the volume of each slice is calculated. Then SUVmean of each slice is multiplied by the volume of the corresponding slice, which will represent the total FDG uptake in one slice. This product for each slice is summed over number of slices to provide GLG of that lung for each subject/patient as follows:

$$GLG = \sum_1^n (area * slice\ thickness * SUV\ mean)$$

n=number of slices

Intra-subject/patient variability (reproducibility measurement (Part 1)) :

Below is the calculation to determine the intra-individual variability between PET/CT scans as measured by GLG for HC subjects and patients with eosinophilic asthma. The accepted variability within each group is  $\leq 10\%$  and will be calculated as follows:

Relative difference of **GLG (HCs)** =  $(GLG2-GLG1)/GLG1$  (For HC subjects)

Relative difference of **GLG (patients with eosinophilic asthma)** =  $(GLG4-GLG3)/GLG3$  (For patients)

1= First measurement (HCs)

2= Second measurement (HCs)

3= First measurement (patients with eosinophilic asthma)

4= Second measurement (patients with eosinophilic asthma)

A 10% variability (measured as a relative difference between the first measurement and second measurement) between PET/CT scans as measured by GLG within each group (HCs, n=5) and patients (n=10), will be considered as the maximum allowed intra-group variability.

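### The Part 1 reproducibility rule is calculated as a signed, one-sided change, while inclusion criterion k limits the size of the difference; as calculated, pass or fail depends on scan order

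*Protocol*

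**What the plan says.** **The formula.** Protocol 6.1.3 gives "Relative difference of GLG=(GLG2-GLG1)/GLG1" for healthy controls and "Relative difference of GLG=(GLG4-GLG3)/GLG3" for asthma patients, with accepted variability of at most 10%. SAP 6.2.1 repeats both formulas and describes the limit as "A 10% variability (measured as a relative difference between the first measurement and second measurement) between PET/CT scans". Neither document writes an absolute value or a limit of -10%.

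**The randomisation step.** Protocol 3.14.3.1 qualifies a patient when Delta GLG is at most 10%, "versus V2 (for reproducibility) and 2") at least 5% against healthy controls. Footnote k of Protocol Table 2 and footnote k of SAP Table 1 state the same step.

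**The eligibility wording.** Inclusion criterion k (Protocol 4.1) requires that the visit 2 and visit 3 GLG measures "differs by only" 10% or less. Protocol 3.1 says that 10% variability "within each group will be considered as the maximum allowed variability". Both describe a size, whichever scan is higher.

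**Where the rule is used.** It gates randomisation. It also feeds the trigger for reevaluating the study, which SAP 2.1 sets at "8 or more asthma patients do not meet the criteria to enter Part 2". The SAP Introduction says that the SAP prevails where the two documents differ, but the SAP carries the same signed formula.

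**The concern.** A reproducibility check should ask how far apart two readings are. The only formula given asks whether the second reading rose by more than 10%. A patient whose GLG falls by 40% between scans qualifies, and one whose GLG rises by 11% does not.

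A programmer cannot settle the sign from context. Protocol 6.1.3 uses the same label and the same form for the comparison with healthy controls, where the sign must stay if the aim is patient above control. The randomisation step uses Delta GLG, which the protocol's abbreviation list defines as change from baseline and for which SAP 6.2.1 gives a signed formula in Part 2.

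Two people could therefore apply different gates to the same scans, which affects:

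- who is randomised;
- the count behind the reevaluation trigger;
- one of the two checks behind primary objective 1;
- the Part 2 GLG baseline, which SAP 4.2 sets as the average of visits 2 and 3. A passing pair of 100 and 60 would enter the primary endpoint as a baseline of 80.

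A lesser point is that Summary 15.2.1.1 describes the signed differences. Rises and falls cancel in their mean, so the mean and median show drift between scans and not reproducibility.

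**Working it through.** The 10% limit comes from expert opinion and has no derivation, so there is no plan figure to reproduce.

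**Step 1: arithmetic that needs no assumption.** Let d = (second - first)/first.

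| First, second | d | Signed rule (d <= 10%) | Absolute rule (size of d <= 10%) |
|---|---|---|---|
| 100, 130 | +30.0% | fail | fail |
| 130, 100 | -23.1% | pass | fail |
| 100, 60 | -40.0% | pass | fail |
| 60, 100 | +66.7% | fail | fail |
| 100, 111 | +11.0% | fail | fail |
| 111, 100 | -9.9% | pass | pass |

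Under the signed rule, every pair whose larger-to-smaller ratio exceeds 1.10 passes in one order and fails in the other. Under the absolute rule, order matters only for ratios above 1.10 and up to 1/0.9 = 1.11, because the denominator is the first scan.

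**Step 2: how often it matters.** The documents give no within-subject CV, so I assume 3%, 5%, 10% or 15%, with lognormal scan error and no true change. The log ratio of the two scans then has SD s = sqrt(2 ln(1 + CV^2)).

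- Signed pass rate: Phi(ln 1.1/s)
- Absolute pass rate: Phi(ln 1.1/s) - Phi(ln 0.9/s)
- Share of signed passers with a fall above 10%: Phi(ln 0.9/s)/Phi(ln 1.1/s)
- Order-dependent pairs, signed rule: 2(1 - Phi(ln 1.1/s))
- Order-dependent pairs, absolute rule: 2(Phi(-ln 0.9/s) - Phi(ln 1.1/s))

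At CV 10%, s = 0.1411, ln 1.1/s = 0.676 and ln 0.9/s = -0.747. The signed pass rate is Phi(0.676) = 75.0%, and the absolute pass rate is 75.0% - Phi(-0.747) = 52.3%.

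| Assumed CV | 3% | 5% | 10% | 15% |
|---|---|---|---|---|
| Pass, signed | 98.8% | 91.1% | 75.0% | 67.4% |
| Pass, absolute | 98.1% | 84.3% | 52.3% | 36.6% |
| Signed passers with a fall above 10% | 0.7% | 7.5% | 30% | 46% |
| Order-dependent, signed | 2.5% | 18% | 50% | 65% |
| Order-dependent, absolute | 1.2% | 4.1% | 4.4% | 3.4% |

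**Step 3: the reevaluation trigger.** The documents give no denominator for the 8 failures. Take 10 patients assessed and criterion l always met, so the chance is P(Binomial(10, 1 - pass rate) >= 8). At CV 10% it is 0.04% signed and 4.0% absolute; at CV 15%, 0.3% and 23%. It is negligible under both rules at CV 3% to 5%. If failures instead accumulate until 10 patients are randomised, the CV 10% figures become about 4% signed and 62% absolute.

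**Step 4: what the signed summary shows.** Simulating 200,000 groups of each size gave:

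| Assumed CV | 3% | 5% | 10% | 15% |
|---|---|---|---|---|
| Typical size of signed group mean, n = 5 | 1.5% | 2.5% | 5.1% | 7.9% |
| Typical size of signed group mean, n = 10 | 1.1% | 1.8% | 3.7% | 5.7% |
| Mean absolute difference | 3.4% | 5.7% | 11.3% | 17.1% |

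The signed mean is less than half the typical scan-to-scan difference in every column.

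**The case against.** The strongest reply is that nobody would read the rule as one-sided. The formula sits under a heading about intra-patient variability, the limit is placed on variability, and variability is a size. Protocol 3.1 and SAP 6.2.1 use relative difference and maximum allowed variability in the same sentence. Criterion k is the formal eligibility rule, and the reevaluation trigger cites it by letter. On this view only a pair of absolute-value bars is missing.

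That reading of intent is very probably right. It does not repair the rule. The only computable statement is signed, the randomisation step repeats it as an upper bound, and the SAP, which prevails, carries it too.

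Other points stand in part:

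- A 40% fall would be rare: probability about 0.00015 at CV 10% under the same model. It shows the mechanism and not a typical case. Falls just beyond 10% are the practical issue.
- All frequencies rest on an assumed CV, and the trigger figures also on an assumed denominator.
- The absolute rule with a first-scan denominator leaves a little order dependence, about 4% of pairs at CV 5% to 10%. Dividing by the mean of the two scans would remove it.
- Signed mean with SD and range is a recognised repeatability summary. The planned SD, range and listings (SAP 4.1 and 6.2.2) keep the noise visible, so the point about Summary 15.2.1.1 is secondary.
- The study is exploratory with no inferential testing, and the gate is common to both arms.

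**Conclusion.** The concern holds. The operational formula and the matching randomisation step do not implement criterion k. As calculated, no fall can fail, and any pair with a ratio above 1.10 changes verdict when the scan order is reversed. This part needs no assumption.

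The practical size depends on scan noise that the documents do not report. It is trivial at CV 3%. At CV 5% the signed and absolute pass rates differ by 7 percentage points, at CV 10% by 23, and at CV 15% by 31, given lognormal error and no true change.

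The conflict affects who enters Part 2, the reevaluation count and the evidence for primary objective 1. It does not by itself bias the treatment comparison. It should be fixed, because the rule decides randomisation and the correction is small.

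**What to change.** Define the criterion per individual as |second - first|/first <= 10% in five places: Protocol 6.1.3, Protocol 3.14.3.1, Protocol Table 2 footnote k, SAP 6.2.1 and SAP Table 1 footnote k. This keeps the existing 10% limit and first-scan denominator; state that order then matters only for ratios between 1.10 and 1.11. Keep criterion l signed, with the patient above the healthy-control mean.

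In Summary 15.2.1.1 add two rows for each group: the mean absolute percent difference, and the number of participants within 10%.

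The drafting cost is five text edits and two summary rows. The operational cost is more failures on criterion k. On that criterion alone, patients scanned per 10 randomised (10 divided by the pass rate) change as follows:

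| Assumed CV | Signed | Absolute |
|---|---|---|
| 3% | 10.1 | 10.2 |
| 5% | 11.0 | 11.9 |
| 10% | 13.3 | 19.1 |
| 15% | 14.8 | 27.4 |

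The reevaluation trigger also becomes easier to reach at CV 10% or more, so the number of patients over which the 8 failures are counted should be stated at the same time.
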